#### **10.2.5 Disease Control Rate**

The disease control rate (DCR) is defined as the percentage of subjects achieving a confirmed CR, PR, or SD out of the total number of subjects included in the analysis population. The CR, PR, or SD must occur prior to PD and the start of any subsequent anticancer therapy. Subjects with not evaluable, unknown, or missing best response will be handled as non-responders; i.e., they will be included in the denominator when calculating the DCR. The independent reviewer-assessed DCR by RECIST v1.1 with 95%, two-sided CIs using the

Idera Pharmaceuticals, Inc.  
Statistical Analysis Plan  
Protocol Number: 2125-MEL-301

---

Wald's binomial method will be provided for each treatment arm. A similar summary will be provided using the investigator-assessed DCR by RECIST v1.1.

The following summaries will be for DCR:

- Independent Reviewer-Assessed DCR by RECIST v1.1
- Investigator-Assessed DCR by RECIST v1.1

### **10.2.6 Duration of Response**

DoR will be derived separately for the assessments by blinded independent reviewer and the investigator. DoR will be derived using RECIST v1.1, defined as the time in months between the date of the first instance of confirmed CR or PR as the best overall response to the day before the first date that recurrent or progressive disease is objectively documented or date of death. For subjects who have attained CR or PR as the best overall response but do not have progressive disease or died, they will be censored at the same time they will be censored for the primary definition of PFS (See [Appendix Section 16.4](#)). Subjects who do not respond will not be included in this analysis.

DoR will be described using Kaplan-Meier estimates with 95% CIs. If there are sufficient number of events, median, first and third quartiles, minimum and maximum for DoR with corresponding 95% CIs will be reported. CIs will be estimated using the Brookmeyer-Crowley method [[Brookmeyer, 1982](#)] with log-log transformation. Summaries will also include the number of subjects at risk, the number of subjects with events, and the number of subjects censored.

The following summaries and figures for DoR will be provided:

- DoR based on Independent Reviewer-Assessed ORR by RECIST v1.1 for ORR Responder
- DoR based on Investigator-Assessed ORR by RECIST v1.1 for ORR Responder
- Kaplan-Meier Plot of DoR based on Independent Reviewer-Assessed ORR by RECIST v1.1 for ORR Responder
- Kaplan-Meier Plot of DoR based on Investigator-Assessed ORR by RECIST v1.1 for ORR Responder

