6.2. Secondary Endpoints

The secondary endpoints include:

- ORR by investigator assessment using RECIST v1.1
- Duration of response (DoR) by blinded independent review and by investigator assessment using RECIST v1.1, measured from the time that criteria are first met for CR or partial response (PR) (whichever is first recorded) until the first date that recurrent or progressive disease is objectively documented
- Durable response rate (DRR) by blinded independent review and investigator assessment (using RECIST v1.1), defined as the rate of CR or PR lasting ≥ 6 months with onset during the first 12 months of treatment
- Time to response, defined as time to a complete or partial response (using RECIST v1.1) measured from the date of randomization, by blinded independent review and investigator assessment
- Progression-free survival (PFS), defined as the time to disease progression or death from any cause measured from the date of randomization, by blinded independent review and investigator assessment (using RECIST v1.1)
- Landmark PFS at 1 and 2 years by blinded independent review and investigator assessment (using RECIST v1.1) and landmark OS at 1 and 2 years
- PRO using the European Organisation for Research and Treatment of Cancer Quality of Life Questionnaire-Core 30 (EORTC QLQ-C30)
- Safety, including AEs, laboratory and vital sign tests, electrocardiograms (ECGs), ECOG, and physical examination
- Plasma PK of IMO2125

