8.3. Study Drug Discontinuation and Study Withdrawal

8.3.1. Subject Discontinuation of Study Drug

Failure to complete Week 10 of study drug (Arm A) or Week 24 (Arm B) for any reason will be considered premature study drug discontinuation. Reasons for premature study drug discontinuation include PD (by irRECIST or by clinical progression), death, intolerable AE, withdrawal of consent, lost to follow up, Investigator discretion, Sponsor decision, and premature termination of the study.

Subjects who discontinue treatment prematurely prior to progression should continue to be followed according to the SOE (Active Follow-up). The Investigator will document the date of and reason(s) for study treatment discontinuation on the electronic case report form (eCRF). Once a subject discontinues study treatment permanently, they will not be able to be retreated.

Subjects who complete the planned study treatment and who have not progressed or started new anti-cancer therapy will enter the Active Follow-up Period and be followed according to the SOE. Subjects will enter the Survival Follow-up Period at disease progression or the start of new anti-cancer therapy (with or without disease progression).

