### **10.2.8 Analysis of Progression-Free Survival**

PFS is defined as the time in months from the date of randomization to progression by RECIST v1.1 or death from any cause. The date of disease progression will be the date of the scan for the first objectively documented PD per RECIST v1.1. Subjects who do not progress including those who have started new anticancer therapy, withdrawn from the study, or been lost to follow-up without disease progression will have their PFS time censored at the last valid disease assessment, defined as a scheduled or unscheduled visit with a disease assessment of CR, PR, or SD (for RECIST v1.1). More detailed censoring rules are in [Appendix Section 16.4](#).

PFS assessed by investigator and independent reviewer will be analyzed using Kaplan-Meier method, the median, first and third quartiles with corresponding 95% CIs are calculated by the Brookmeyer-Crowley method with log-log transformation. If there are a sufficient number of events, Kaplan-Meier estimates and 95% CIs will also be produced at PFS landmark time points at 6 months, 1 and 2 years. The 95% CIs for Kaplan-Meier estimates at each of the PFS landmark time points will be calculated using Greenwood's formula with log-log transformation. Summaries will also include the number at risk, the number of subjects with events, and the number of subjects censored along with their corresponding reason for censoring. Figures will use the Kaplan-Meier estimates and identify the number of subjects at risk at each scheduled visit and censored times on the curve.

The following summaries and figures will be provided for PFS:

- Summary of Independent Reviewer-Assessed PFS by RECIST v1.1
- Summary of Investigator-Assessed PFS by RECIST v1.1
- Kaplan-Meier Plot of Independent Reviewer-Assessed PFS by RECIST v1.1
- Kaplan-Meier Plot of Investigator-Assessed PFS by RECIST v1.1

The following efficacy listing will be provided:

- Progression-free Survival by Independent Reviewer-Assessed and Investigator-Assessed RECIST v1.1

Idera Pharmaceuticals, Inc.  
Statistical Analysis Plan  
Protocol Number: 2125-MEL-301

---

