## 16.4 CENSORING RULE FOR PFS

The following censoring rules will be used for PFS analysis to be consistent with FDA guidance on Clinical Trial Endpoints for the Approval of Cancer Drugs and Biologics.

[source: <https://www.fda.gov/downloads/Drugs/Guidances/ucm071590.pdf>]

Situation	Date of Progression or Censoring	Outcome
No baseline tumor assessments	Randomization	Censored
Progression documented between scheduled visits	Earliest of: 
 
• Dates of target lesion scans when the target lesion response is PD;
 
or
 
• Dates of non-target scans at which the non-target lesion status is unequivocal progression;
 
or
 
• Dates of scans documenting new lesion (if progression is based on new lesion)
 
	Event
No progression	Date of the last valid disease assessment, defined as a scheduled or unscheduled visit with a disease assessment of CR, PR, or SD	Censored
Treatment discontinuation for undocumented progression	Date of the last valid disease assessment, defined as a scheduled or unscheduled visit with a disease assessment of CR, PR, or SD	Censored
Treatment discontinuation for other reasons	Date of the last valid disease assessment, defined as a scheduled or unscheduled visit with a disease assessment of CR, PR, or SD	Censored
New anticancer treatment started	Date of the last valid disease assessment, defined as a scheduled or unscheduled visit with a disease assessment of CR, PR, or SD, prior to new anticancer treatment started	Censored
Death without documented progression and is not after two or more missed visits	Date of death	Event
Death or progression after two or more missed visits	Date of the last valid disease assessment, defined as a scheduled or unscheduled visit with a disease assessment of CR, PR, or SD	Censored

Idera Pharmaceuticals, Inc.  
Statistical Analysis Plan  
Protocol Number: 2125-MEL-301

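### SAP 10.2.6 lets duration of response run to a death after scans have stopped, where PFS for the same subject is censored at the last valid assessment

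*SAP*

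**What the plan says.** - **End of response, SAP 10.2.6.** DoR runs "to the day before the first date that recurrent or progressive disease is objectively documented or date of death". Neither new therapy nor missed visits limits which deaths or progressions count.
- **Censoring, SAP 10.2.6.** Responders who "do not have progressive disease or died, they will be censored at the same time they will be censored for the primary definition of PFS" are referred to Appendix 16.4. A responder who died or progressed is not in that group.
- **PFS, SAP 10.2.8 and Appendix 16.4.** "PFS is defined as the time in months from the date of randomization to progression by RECIST v1.1 or death from any cause", subject to the appendix. The row "New anticancer treatment started" censors at the last valid assessment before that treatment. The row "Death or progression after two or more missed visits" also censors at the last valid assessment. Death without documented progression is an event only if it does not follow two or more missed visits.
- **Follow-up, Protocol 8.3.1.** "Subjects will enter the Survival Follow-up Period at disease progression or the start of new anti-cancer therapy (with or without disease progression)". Protocol Tables 1 and 2 then provide telephone contact every 3 months, so deaths are still collected after scans have ended.
- **Protocol definition of DoR, 6.2 and 15.4.2.** Response lasts "until the first date that recurrent or progressive disease is objectively documented". Death is not mentioned. SAP 5 nevertheless reports no difference from the protocol's planned analyses.

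**The concern.** DoR and PFS are meant to describe the same disease course, one from response and the other from randomization. A subject's response should not outlast that subject's PFS. As written it can, because the limits that protect PFS from unobserved time are not carried into DoR once the responder has died or progressed.

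The protocol makes such records possible: imaging ends when new therapy starts, with or without progression, while survival is still followed. The independent-review analysis has a further route. Progression called only by the investigator moves the subject to survival follow-up with no reviewer progression on record. PFS is then censored for a later death if new therapy was started or if the scans not done are counted as missed visits.

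Censoring also comes to depend on outcome. Of two responders whose scans stop on the same day, the one still alive at cut-off is censored at the last scan, and the one who dies is carried forward to death. The second duration includes time without imaging and possibly time under another treatment. DoR is a named secondary endpoint, and both DoR tables are marked as topline outputs in SAP 16.2.

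**Working it through.** The plan states no DoR figure to reproduce, so the check applies the written rules to example subjects and then asks how many might be affected.

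**1. Individual records.** Days are divided by 30.4375 (SAP 8.2.4); one-day conventions are ignored. The dates are assumed but lie on or between the scheduled scans (Week 12, then every 8 weeks in year 1). No subject has progression by the given assessor, and each starts new therapy after the last scan or misses at least two visits.

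| Response / last valid scan / death (weeks) | PFS, Appendix 16.4 | DoR as written | DoR with all 16.4 rows |
|---|---|---|---|
| 12 / 28 / 104 | 28×7/30.4375 = 6.4, censored | 92×7/30.4375 = 21.2, event | 16×7/30.4375 = 3.7, censored |
| 12 / 28 / 52 | 6.4, censored | 40×7/30.4375 = 9.2, event | 3.7, censored |
| 28 / 52 / 130 | 52×7/30.4375 = 12.0, censored | 102×7/30.4375 = 23.5, event | 24×7/30.4375 = 5.5, censored |

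If the second subject had progression found at Week 52 instead of death, the contrast would be the same: a DoR event at 9.2 months against PFS censored at 6.4.

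**2. General condition.** DoR exceeds PFS when (death − response) > (last scan − randomization), that is, when death follows the last valid scan by more than the time to response. For a Week 12 responder that is more than 12 weeks. Two missed year-1 visits already span about 16 weeks.

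**3. Outcome dependence.** If the first subject were alive at cut-off, DoR would be censored at 3.7 months. Because the subject died at Week 104, it is an event at 21.2 months. The scans are identical in both cases.

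**4. How many responders.** The documents give no rate at which scans stop before progression, so this part rests on assumptions:
- median 12 months from response to progression;
- 15-40% of responders with a potential scan stop, uniform at 1-9 months;
- median 9-18 months from stop to death;
- follow-up of 24-44 months.

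Scans then stop before progression in about 11-30% of responders. Those who also die before cut-off are about 8-27%. The planned response rates give 0.24×227 = 54.5 and 0.12×227 = 27.2 responders, taken as 54 and 27. The affected numbers are 0.08×54 = 4.3 to 0.27×54 = 14.6, and 0.08×27 = 2.2 to 0.27×27 = 7.3; rounded down, 4-14 and 2-7 subjects.

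A death within about 16 weeks of the stop, with no new therapy, may remain a PFS event. Removing all deaths that early leaves about 6-19% (3.2-10.3 and 1.6-5.1 subjects).

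**5. Effect on the median.** In these scenarios the Kaplan-Meier median DoR shifts by −0.1 to −1.1 months against PFS-consistent censoring. A second assumed set (response at Week 12, 10-40% assigned to stop scans early, median 18 months from stop to death, 30-month cut-off) gives medians of 11.7-12.0 against 12.0-12.1 months. DoR exceeds PFS in 3.2% to 13.5% of responders. The median does not rise, because each late death adds an event where there would otherwise be a censored time.

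**The case against.** The best defence is that alignment with PFS was probably intended. SAP 10.2.6 cites Appendix 16.4, the SAP's modification history says version 3.0 clarified the DoR censoring rule, and SAP 8.2 leaves full derivations to separate dataset specifications. DoR is descriptive (Protocol 15.4.2, SAP 7.2), its median barely moves, and censoring at new therapy is itself a choice that can be informative. Management by irRECIST, with confirmation of progression, also tends to extend imaging. All of this limits the consequence. It does not change the text, which leaves deaths and late progressions outside the censoring table; a programmer following it would produce the durations shown above.

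Several stronger readings are tempting but not supported:
- **Any later death extends DoR.** No. Progression documented earlier by the same assessor ends the response.
- **Every responder whose scans stop has a wrong duration.** No. Those with neither progression nor death at cut-off are censored as for PFS.
- **The durable response rate (DRR) is inflated.** SAP 10.2.4 defines DRR separately, with its own start and a 182.625-day cut-off. It does not cite 10.2.6 or name death as an end. An effect arises only if the DoR duration is reused.
- **The swimmer's plots are wrong.** SAP 10.1.1 and 10.2.1 give only their titles, so the duration plotted is unknown.
- **The SAP starts DoR later than the protocol.** The phrase "the first instance of confirmed CR or PR as the best overall response" could be read as starting at a later CR in a subject who first had PR. It can equally be read as identifying who is a responder, which is how the next sentence of 10.2.6 uses best overall response. This is an ambiguity, not an error.

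**Conclusion.** The point holds for responders without earlier documented progression by the given assessor who start new therapy or miss two or more visits and then die, and for progression found after either. For them DoR and PFS follow different rules, and DoR can exceed PFS by many months (21.2 against 6.4 in the first example). Individual durations, event counts and the maximum are affected, and censoring depends on outcome. The median moves little and no hypothesis test is affected.

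The incoherence follows from the text alone. The frequency does not: 8-27% of responders, or fewer if early deaths remain PFS events, rests entirely on the assumed scan-stop and survival times. Separately, the SAP's death event is a departure from the protocol's definition that SAP 5 does not record.

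**What to change.** - In SAP 10.2.6, apply all event and censoring rows of Appendix 16.4 to every responder, including those who die or progress after new anticancer therapy or after two or more missed visits. Such subjects are then censored at the last valid assessment, as for PFS.
- In SAP 5, record that the SAP adds death as a DoR event to the definition in Protocol 6.2 and 15.4.2.
- As a wording clarification, start DoR at the first documentation of a subsequently confirmed CR or PR, whichever is recorded first, as the protocol does.
- If DRR is to use the DoR duration, say so in SAP 10.2.4 and apply the same rule.

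The cost is SAP wording and one derivation change. The downside is a few more censored responders.

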### **10.2.7 Time to Response**

TTR will be derived as the time in months from the date of randomization to date of the scan for the first instance of confirmed CR or PR (using RECIST v1.1) by investigator and independent reviewer assessments. Subjects who do not respond will not be included in this analysis.

Idera Pharmaceuticals, Inc.  
Statistical Analysis Plan  
Protocol Number: 2125-MEL-301

---

TTR will be summarized descriptively with mean, standard deviation, median, minimum and maximum.

The following summaries will be provided:

- TTR based on Independent Reviewer-Assessed ORR by RECIST v1.1 for ORR Responder
- TTR based on Investigator-Assessed ORR by RECIST v1.1 for ORR Responder

### **10.2.8 Analysis of Progression-Free Survival**

PFS is defined as the time in months from the date of randomization to progression by RECIST v1.1 or death from any cause. The date of disease progression will be the date of the scan for the first objectively documented PD per RECIST v1.1. Subjects who do not progress including those who have started new anticancer therapy, withdrawn from the study, or been lost to follow-up without disease progression will have their PFS time censored at the last valid disease assessment, defined as a scheduled or unscheduled visit with a disease assessment of CR, PR, or SD (for RECIST v1.1). More detailed censoring rules are in [Appendix Section 16.4](#).

PFS assessed by investigator and independent reviewer will be analyzed using Kaplan-Meier method, the median, first and third quartiles with corresponding 95% CIs are calculated by the Brookmeyer-Crowley method with log-log transformation. If there are a sufficient number of events, Kaplan-Meier estimates and 95% CIs will also be produced at PFS landmark time points at 6 months, 1 and 2 years. The 95% CIs for Kaplan-Meier estimates at each of the PFS landmark time points will be calculated using Greenwood's formula with log-log transformation. Summaries will also include the number at risk, the number of subjects with events, and the number of subjects censored along with their corresponding reason for censoring. Figures will use the Kaplan-Meier estimates and identify the number of subjects at risk at each scheduled visit and censored times on the curve.

The following summaries and figures will be provided for PFS:

- Summary of Independent Reviewer-Assessed PFS by RECIST v1.1
- Summary of Investigator-Assessed PFS by RECIST v1.1
- Kaplan-Meier Plot of Independent Reviewer-Assessed PFS by RECIST v1.1
- Kaplan-Meier Plot of Investigator-Assessed PFS by RECIST v1.1

The following efficacy listing will be provided:

- Progression-free Survival by Independent Reviewer-Assessed and Investigator-Assessed RECIST v1.1

Idera Pharmaceuticals, Inc.  
Statistical Analysis Plan  
Protocol Number: 2125-MEL-301

---

## 11 SAFETY ANALYSES

All safety analyses will be based on the Safety Set as defined in [Section 6.5](#). Summaries of AEs will include only treatment-emergent AEs (TEAEs), defined as AEs with a start date on or after the date of first dose of study treatment or existing AEs which increase in CTCAE grade after the start of study treatment. If it cannot be determined definitively whether the AE is treatment emergent due to missing or partial onset or end dates, then it will be counted as treatment emergent (see [Section 8.2.7](#) for details).

### 11.1 EXTENT OF EXPOSURE

Overall exposure will be summarized descriptively by treatment arm and separately by study drug. For ipilimumab, summaries will include the number of infusions received, duration of treatment (weeks), cumulative dose received in milligrams per kilogram (mg/kg) and average dose (mg/kg), per infusion. For IMO-2125, summaries will include the number of injections received, type of injected lesions per eCRF category (i.e., Superficial, Other deep soft tissue, Organ, and Other), duration of treatment (weeks), the cumulative dose received in milligrams (mg), and the average dose (mg) per injection.

To summarize type of injected lesions per eCRF category, subjects will be counted under each type of injection if the subjects received more than one type of injection. Furthermore, the type of injected lesions will also be reclassified into 3 categories: Superficial, Deep, or Visceral (Organ). The Sponsor will perform a review of the 'Other' injection type and map them to the 3 specified categories. If a subject had more than one type of injected lesion during the study, the deepest type of injection will be counted in the summary. For example, a subject who had both deep and visceral injections will be counted under visceral.

Treatment duration will be calculated in weeks for each subject and each treatment using the following formula: Treatment duration (weeks) = (last dose date - first dose date + 1) / 7.

For IMO-2125, cumulative dose received is calculated as the sum of doses (mg) across all injections, and average dose is calculated as the cumulative dose divided by the sum of injections. For ipilimumab, the dose (mg) divided by base weight (kg) will be derived for each subject at each dosing visit. Cumulative dose received is calculated as the sum of dose per weight (mg/kg) across all infusions, and average dose is calculated as the cumulative dose divided by the sum of infusions.

Dose reductions were permitted for patients dosed under Protocol Version 2.0 only. Any dose modifications of study treatment due to irAE will be listed.

The following summaries will be provided:

Idera Pharmaceuticals, Inc.  
Statistical Analysis Plan  
Protocol Number: 2125-MEL-301

---

- IMO-2125 Exposure
- Ipilimumab Exposure

The following listings will be provided:

- IMO-2125 Exposure
- Ipilimumab Exposure
- Dose Modifications Due to irAEs

